6. DOSAGE AND ADMINISTRATION

A 100 mg/mL solution of CNTO 1959 in a single-use prefilled syringe (PFS) assembled with the UltraSafe PLUS™ Passive Needle Guard (PFS-U) device will be used. Liquid placebo for CNTO 1959 will also be supplied as a PFS assembled with the PFS-U. During the study, all subjects will subcutaneously receive two syringes for each dose.

All study drug administrations will be given at the study site. The dose regimens are as follows:

- **Group I:** Two syringes of CNTO 1959 100 mg at Weeks 0, 4, 12 and q8w thereafter through Week 60, 2 syringes of placebo for CNTO 1959 100 mg at Week 16 to maintain the blind.
- **Group II:** A syringe of CNTO 1959 100 mg and a syringe of placebo for CNTO 1959 100 mg at Weeks 0, 4, 12 and q8w thereafter through Week 60, 2 syringes of placebo for CNTO 1959 100 mg at Week 16 to maintain the blind.
- **Group III:** Two syringes of placebo for CNTO 1959 100 mg at Weeks 0, 4 and 12 to maintain the blind. At Week 16, placebo subjects will be randomized in a 1:1 ratio to CNTO 1959 200 mg arm (Group IIIa) or 100 mg arm (Group IIIb). Group IIIa subjects will receive 2 syringes of CNTO 1959 100 mg at Weeks 16, 20 and q8w thereafter through Week 60. Group IIIb subjects will receive a syringe of CNTO 1959 100 mg and a syringe of placebo for CNTO 1959 100 mg at Weeks 16, 20 and q8w thereafter through Week 60.

7. TREATMENT COMPLIANCE

Because study drug will be administered at the investigational site for all randomized subjects, treatment compliance will be controlled by site personnel.

The Week 2 and 4 visits should occur within ± 3 days of the scheduled visit date. All the other study visits should occur within ± 7 days of the scheduled visit date. If a study visit occurs outside this window, the subject should then resume his or her normal dose schedule relative to the baseline visit (Week 0).

Information regarding study drug administrations that are administered outside of the scheduled windows or missed will be recorded. Subject charts and worksheets will be reviewed and compared with the data entries on the eCRFs to ensure accuracy. Although it is understood that treatment may be interrupted for many reasons, compliance with the treatment schedule is strongly encouraged.

8. CONCOMITANT THERAPY

Any concomitant therapy that could affect palmoplantar pustulosis or the efficacy evaluation and would be used for serious adverse events must be recorded throughout the study from screening until the study end. Other concomitant therapies must be recorded throughout the study from screening and continuing until 12 weeks after the last dose of study drug for randomized subjects.

All therapies (prescription or over-the-counter medications, including vaccines, vitamins, herbal supplements) different from the study drug must be recorded in the eCRF. Modification of an effective preexisting therapy should not be made for the explicit purpose of entering a subject into the study.

8.1. Week 0 through Week 60

8.1.1. Concomitant Medications for Treatment of Palmoplantar Pustulosis

8.1.1.1. Topical Therapy

Topical therapies that could affect palmoplantar pustulosis or the efficacy evaluation (eg, corticosteroids, vitamin D3 derivatives, tacrolimus, and antibiotics) are not permitted. The only allowable concomitant treatments for palmoplantar pustulosis throughout the study are topical moisturizers including horny softener. Subjects should not use moisturizers on the day of a study visit.

8.1.1.2. Focal infection treatment, Phototherapy or Systemic medications for Palmoplantar Pustulosis

Focal infection must be carefully assessed in all subjects, and the focal infection treatment should be completed before starting the study. Focal infection treatments for palmoplantar pustulosis (e.g., tonsillectomy) are not permitted at any time during the study. If tooth abscess and/or tooth cavity is newly recognized after starting the study, dental therapy could be allowed.

The use of phototherapy or systemic medications for palmoplantar pustulosis are not permitted at any time during the study. These medications include those targeted for reducing TNF (including but not limited to infliximab, adalimumab or etanercept), drugs targeted for reducing IL-12, IL-17, or IL-23 (including but not limited to ustekinumab, tildrakizumab [MK3222], secukinumab [AIN457], ixekizumab [LY2439821], or brodalumab [AMG827]), alpha-4 integrin antagonists (including but not limited to natalizumab), steroids, any conventional systemic therapy that could affect palmoplantar pustulosis or the efficacy evaluation (including but not limited to vitamin D3 derivatives, antibiotics, biotin, MTX, cyclosporine, etretinate), herbal treatments, or traditional Taiwanese, Korean, or Chinese medicines, and any other biological agent or other systemic medication that could affect palmoplantar pustulosis or the efficacy evaluation.

8.1.1.3. Concomitant Medications for PAO

The use of nonsteroidal anti-inflammatory drugs for PAO is allowed.

The use of corticosteroids for PAO should be limited to situations for which, in the opinion of the treating physician, there are no adequate alternatives. They should be used on a short-term

basis, preferably for ≤ 2 weeks. Longer-term use of corticosteroids should be discussed with the medical monitor or designee and may require discontinuation of study drug.

Any other therapies that could affect palmoplantar pustulosis or the efficacy evaluation (eg, bisphosphonates, immunosuppressants [eg, methotrexate, azathioprine, cyclosporine, 6-thioguanine, mercaptopurine, mycophenolate mofetil, tacrolimus]) or anakinra are not permitted.

8.1.2. Concomitant Medications for Conditions Other than Palmoplantar Pustulosis

Every effort should be made to keep subjects on stable concomitant medications. If the medication is temporarily discontinued because of abnormal laboratory values, side effects, concurrent illness, or the performance of a procedure, the change and reason for it should be clearly documented in the subject's medical record.

The use of nonsteroidal anti-inflammatory drugs is allowed. However, disease-modifying agents such as MTX, sulfasalazine, or IM gold are prohibited during the study. Antimalarial agents, with the exception of chloroquine, may be used after Week 60.

The use of corticosteroids for indications other than palmoplantar pustulosis should be limited to situations for which, in the opinion of the treating physician, there are no adequate alternatives. They should be used on a short-term basis, preferably for ≤ 2 weeks. Longer-term use of corticosteroids should be discussed with the medical monitor or designee and may require discontinuation of study drug. Topical medication to body area other than palms and soles, inhaled, otic, ocular, nasal or other routes of mucosal delivery of corticosteroids are allowed throughout the study.

8.2. After the week 60

After the Week 60 visit, there is no limitation on concomitant therapies.

The sponsor must be notified in advance (or as soon as possible thereafter) of any instances in which prohibited therapies are administered.

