After Week 60 until Week 84 (Observational Period)

[figure not shown]
The observational period will begin from Week 60 and extend until Week 84. All subjects will no longer receive the study drug during the observational period. Efficacy and safety will be evaluated at Week 72, and the durability of clinical response and safety at Week 84.

The investigators and subjects will be unblinded after the last subject has completed the Week 60 visit. The end of the study is defined as the time when the last subject completes the Week 84 visit. Database locks will occur at Weeks 16, 24, 52 and 84. Additional DBLs may also occur after Week 52 DBL during the study.

A serum sample for biomarkers will be collected from all subjects.

A diagram of the study design is provided below in [Figure 1](#). When approximately 40% of the 150 randomized subjects have completed Week 16 visit or have ended study participation before Week 16 visit, an interim analysis is planned to be conducted to re-estimate the sample size and determine whether to stop the study early for futility. An Independent Data Monitoring Committee (IDMC) will be constituted for safety monitoring and interim analysis review of this study.

Figure 1: Study design

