9.1.4. Observational Period (Week 60 through Week 84)

At Week 72, Subjects will be followed for safety and PK and immunogenicity information, Subjects will be followed for safety, and maintenance of efficacy information during the observational period (Week 60 through Week 84) as per the [TIME AND EVENTS SCHEDULE](#).

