10. SUBJECT COMPLETION/WITHDRAWAL

10.1. Completion

A subject will be considered to have completed the study if he or she has completed assessments at Week 60 of the treatment phase. Subjects who prematurely discontinue study treatment for any reason before completion of the treatment phase will not be considered to have completed the study.

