To account for a larger common standard deviation, assuming a fixed 5.5 difference between groups and a common SD of 10, the required number of patients per group for a 90% power is 75. Meanwhile, an evaluable long-term safety population for CNTO 1959 is considered to have at least 50 patients per group. Therefore, the study design is pre-planned as 50 patients per group but with the option of an adaptive sample size re-estimation with a maximum allowable sample size of 75 patients per group (225 in total).

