11.3.2. Efficacy Definitions

Treatment Failure: Subjects who discontinue study treatment due to lack of efficacy or an AE of worsening of Palmoplantar Pustulosis, or who started a protocol-prohibited medication/therapy during the study that could improve Palmoplantar Pustulosis are considered treatment failures. The treatment failure rules and handlings of efficacy data for patients with treatment failure will be documented in detail in the SAP.

PPPASI 50 Responders: Subjects with $\geq 50\%$ improvement in PPPASI from baseline will be considered PPPASI 50 responders.

PPPASI 75 Responders: Subjects with $\geq 75\%$ improvement in PPPASI from baseline will be considered PPPASI 75 responders.

PPPASI 90 Responders: Subjects with $\geq 90\%$ improvement in PPPASI from baseline will be considered PPPASI 90 responders.

PPPASI 100 Responders: Subjects with 100% improvement in PPPASI from baseline will be considered PPPASI100 responders (ie, PPPASI score = 0).

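### Limits on concomitant therapy after Week 60 are worded inconsistently, and on the likelier reading response to newly started therapy can be summarised as durable response to CNTO 1959 at Weeks 72 and 84

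*Protocol*

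**What the plan says.** Protocol Section 8.2 covers the time after Week 60 and states: "After the Week 60 visit, there is no limitation on concomitant therapies". Its next sentence asks sites to notify the sponsor whenever prohibited therapies are given.

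The bans themselves stand under the heading "8.1. Week 0 through Week 60". Their sentences carry no such end date:
- Section 8.1.1.1 allows only moisturisers as PPP treatment for the length of the study.
- Section 8.1.1.2 rules out phototherapy, systemic PPP medication and focal infection treatment at any point in the study.
- Section 8.1.2 prohibits disease-modifying agents for the study. It also says that antimalarials other than chloroquine may be used once Week 60 has passed.

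Two passages bear on when the study ends. Section 10.1: "A subject will be considered to have completed the study if he or she has completed assessments at Week 60 of the treatment phase". Section 3.1: "The end of the study is defined as the time when the last subject completes the Week 84 visit".

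Two definitions in Section 11.3.2 depend on this. Subjects "who started a protocol-prohibited medication/therapy during the study that could improve Palmoplantar Pustulosis are considered treatment failures"; so are those who stop study treatment for lack of efficacy or an adverse event of worsening PPP. Subjects with at least 50% "improvement in PPPASI from baseline will be considered PPPASI 50 responders". The detailed failure rules are left to the SAP.

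Section 2.1 makes durability of response by dose level a secondary objective. Section 3.1 names Week 84 as the visit for it, and Section 9.1.4 assigns Weeks 60 to 84 to maintenance of efficacy.

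**The concern.** The failure definition takes its meaning from the list of prohibited therapies, and the protocol is not consistent on how long that list applies. The inconsistency falls in the one period in which durability off drug is measured.

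If nothing is prohibited after Week 60, a subject whose disease returns and who then starts another PPP treatment is not a failure under the stated definition. If that treatment works, the subject meets the responder definition at Week 72 or 84. The result would be read as durable response to CNTO 1959 when it is response to something else. Subjects losing response are plausibly the ones who start new therapy, so the error would tend to flatter durability.

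**Working it through.** The protocol gives no figure to reproduce on this point, so the check sets the passages side by side.

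**Step 1. When do the bans end?**

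| Points to Week 60 | Points beyond Week 60 |
|---|---|
| Heading of 8.1 | Whole-study wording in 8.1.1.1, 8.1.1.2 and 8.1.2 |
| Opening sentence of 8.2 | Chloroquine exception in 8.1.2, expressly about the time after Week 60 |
| Subject completion at Week 60 (10.1) | Mention of prohibited therapies inside 8.2 |
| | Study end at Week 84 (3.1) |

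The layout favours Week 60: two adjacent sections, each labelled with its period. The chloroquine sentence is the sharpest conflict, because it speaks of the post-Week-60 period by name and keeps a limit that 8.2 says does not exist.

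**Step 2. One subject under each reading.** Take a subject who finishes dosing at Week 60, starts a PPP therapy at, say, Week 66, and shows 50% improvement in PPPASI from baseline at Week 84.

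| | Bans end at Week 60 | Bans run to Week 84 |
|---|---|---|
| Stopped study treatment for lack of efficacy or worsening? | No; the last dose was at Week 60 | No |
| Started a prohibited therapy? | No; nothing is prohibited | Yes, if the therapy is on the list |
| Failure under 11.3.2? | No | Yes |
| Meets the PPPASI 50 definition? | Yes; it sets no condition on other therapy | Overridden by failure status, subject to the SAP |
| Other effect | None | Section 10.3 could also call for withdrawal |

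**Step 3. Which results are reached?** The Time and Events Schedule has PPPASI, PPSI and PGA at Weeks 72 and 84, and the over-time endpoints in 9.2.2 take in those visits. Section 11.3.5 limits MMRM analyses and tests of binary variables to data through Week 16, so what remains at Weeks 72 and 84 is descriptive. The Week 16 primary and major secondary analyses, the Type I error and the sample size are untouched.

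**Step 4. Scale.** The protocol states no rate of new PPP therapy after Week 60, so no shift can be estimated. The only available arithmetic is the weight of one subject, 1/n. The design is "pre-planned as 50 patients per group but with the option of an adaptive sample size re-estimation" up to 75, and placebo subjects are split 1:1 at Week 16:
- Groups I and II: 1/50 = 2.0 points; at the maximum, 1/75 = 1.3 points.
- Groups IIIa and IIIb: 50/2 = 25 each, and 1/25 = 4.0 points.

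These values would hold for any reclassified subject, whatever the cause. They convert counts to points and do not measure this problem. Actual denominators will be smaller after dropout, since 11.3.1 bases most secondary summaries on subjects with evaluable measurements.

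**The case against.** The strongest reply is that the section structure already settles the matter. Section 8.1 is labelled for Weeks 0 to 60 and 8.2 for the time after, so whole-study wording inside 8.1 is loose drafting. The Week 84 end in 3.1 is a trial-level milestone and does not say how long a subject is restricted. Recording therapy until study end, as Section 8 requires, fits equally well with therapy being allowed. Much of this stands: Week 60 is the better reading. It does not dispose of the chloroquine sentence, which conflicts with 8.2 under any reading of the heading.

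A second reply is that the harm arises only on the favoured reading, where most passages agree, and that handling of permitted therapy in a follow-up period belongs in the SAP. The SAP may indeed settle it, and nothing is claimed to be missing. But the trigger is written in the protocol itself: 11.3.2 ties it to prohibition, and under 8.2 prohibition has lapsed by the time durability is assessed. That is a stated rule with an unwanted effect.

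A third reply is that the effect is small, descriptive and recoverable, since Section 8 already has PPP-affecting therapy recorded to study end. That is right, and it sets the severity. It also means that no particular treatment of the continuous endpoints can be required from these documents.

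**Conclusion.** The point holds as a minor one. Section 8.2 conflicts with the chloroquine exception in 8.1.2, with its own mention of prohibited therapies, and with the whole-study wording of three subsections. On the reading the layout favours, the 11.3.2 failure trigger cannot newly apply in Weeks 60 to 84, and response to newly started PPP therapy can enter the durability summaries as response to CNTO 1959. On the other reading the same subject is a failure. The size is unknown; it depends on how many subjects start such therapy and then meet a responder threshold.

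A reader might infer three stronger things that the documents do not support:
- That the two readings are evenly balanced. They are not; the heading of 8.1 and Section 10.1 favour Week 60.
- That a confirmatory result is at risk. No test is planned after Week 16.
- That the protocol fails to say how failures are handled. Section 11.3.2 leaves that to the SAP, which is not at hand.

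The verdict assumes that the SAP does not already key failure at Weeks 72 and 84 to any new PPP therapy. If it does, only the wording conflict remains.

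**What to change.** 1. Reconcile the time scope of 8.1.1.1, 8.1.1.2, 8.1.2 (including the chloroquine sentence) and 8.2 (including its sentence on prohibited therapies). No view is taken here on which therapies should be permitted, or when.
2. For the Week 72 and 84 responder summaries only, count a subject as a failure from the time they start, after the Week 60 visit, any therapy that could improve PPP, whether or not it is prohibited. Section 11.3.2 already uses the idea of a therapy that could improve PPP, so the term is not new. Give the as-observed summary as supportive, and report by dose group how many subjects started such therapy.
3. Leave the Week 0 to 60 failure definition as it is, so that the Week 16 PPPASI-50 analysis does not change. Leave the handling of continuous endpoints at Weeks 72 and 84 to the SAP.

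The cost is a wording clarification and one programming rule for two visits. No new data are needed, because PPP-affecting therapy is already recorded until study end. The downside is that reported Week 72 and 84 response rates may be slightly lower than in an as-observed summary.

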9. STUDY EVALUATIONS

9.1. Study Procedures

9.1.1. Overview

The [TIME AND EVENTS SCHEDULE](#) summarizes the frequency and timing of efficacy, pharmacokinetic, immunogenicity, biomarker, safety, clinical laboratory and other measurements applicable to this study.

Study visit dates are scheduled relative to the Week 0 visit date. The study visits scheduled postrandomization should occur at the times delineated in the [TIME AND EVENTS SCHEDULE](#). The Week 2 and 4 visits should occur within ± 3 days of the scheduled visit date. All the other study visits should occur within ± 7 days of the scheduled visit date.

All visit-specific patient-reported outcome (PRO) assessments should be conducted/completed before any tests, procedures, or other consultations for that visit to prevent influencing subject perceptions.

Additional urine pregnancy tests may be performed, as determined necessary by the investigator or required by local regulation, to establish the absence of pregnancy at any time during the subject's participation in the study.

The total blood volume for the study is approximately 214.0 mL (83.5 mL for Safety, 84.0 mL for PK immunogenicity, 4.0 mL for Population PK, 42.5 mL for Biomarkers). ([Attachment 7](#))

9.1.2. Screening Phase

All subjects will have a screening visit that will occur within approximately 6 weeks before their first drug administration (Week 0). The screening phase is designed to assess inclusion/exclusion criteria and establish baseline characteristics for a subject's palmoplantar pustulosis.

The subjects will be asked to sign the consent form at the screening visit before any study related procedures are conducted.

Adverse events and concomitant medication recording will start after the signing of the informed consent and will continue until the last study-related procedure.

Subjects with a negative IGRA result are eligible to continue with prerandomization procedures. Subjects with a newly identified positive IGRA result must undergo an evaluation to rule out active TB and initiate appropriate treatment for latent TB. Appropriate treatment for latent TB is defined according to local country guidelines for immunocompromised patients (see [Attachment 9](#)).

A subject whose first IGRA result is indeterminate should have the test repeated. In the event that the second IGRA result is also indeterminate, the subject should be excluded from the study.

Subjects must undergo testing for TB ([Attachment 9](#)) and their medical history assessment must include specific questions about a history of TB or known occupational or other personal exposure to individuals with active TB. The subject should be asked about past testing for TB, including chest radiograph results and responses to tuberculin skin or other TB testing.

Subjects will undergo screening for HBV ([Attachment 10](#)) and antibodies to HCV, HIV, and HTLV-1.

Screen Failure/Rescreening

If, during the screening phase, the subject has not met all inclusion criteria or met any exclusion criteria, or is unable or unwilling to adhere to the prohibitions and restrictions of the study, the subject is considered to be a screen failure and is not eligible to be randomized at that time.

If the result of a test does not meet all enrollment criteria, the test may be performed a second time at the discretion of the investigator. In such cases, the first test result will not constitute a screening failure; however, the result of second test that also does not meet all enrollment criteria will be considered a screening failure. A subject will not be randomly assigned to treatment if results of a test performed at screening or baseline, or if applicable, results of a second test indicate that the subject is ineligible to participate.

In general, if a subject is a screen failure, but at some point after screening meets all of the subject eligibility criteria, the rescreening may be performed after new informed consent has been obtained. Subjects who are rescreened will be assigned a new subject number and will restart a new screening phase.

9.1.3. Treatment Phase

Week 0/Day of Randomization

At Week 0, subjects who satisfy all inclusion and exclusion criteria will be randomized. All required tests and evaluations must be conducted before start of study drug administration.

Randomization visit procedures will be performed as specified on the [TIME AND EVENTS SCHEDULE](#).

Post-randomization Visit (Week 2 through Week 60)

All visit procedures will be performed as specified in the [TIME AND EVENTS SCHEDULE](#).

